6.4 Participant Disposition

The number of participants in each analysis population will be presented along with reason for any exclusions. Participant accountability will be summarized by visit. The number of participants who are enrolled, eligible for follow-up, and number completing clinical follow-up will be summarized for each protocol-required visit. In addition, the number of participants who complete the study or exit early will be summarized by reason.

Statistical Analysis Plan		Page 16 of 23
Sponsor Luminopia	Study Luminopia One Amblyopia Vision Improvement Study	

6.5 Demographics and Baseline Characteristics

Descriptive statistics will be presented for all clinically-relevant baseline demographic and medical history variables.

6.6 Analysis of Study Endpoints

6.6.1 Primary Efficacy Endpoint

The mean change in amblyopic eye BCVA from baseline to 12 weeks of treatment with Luminopia One compared to mean change in amblyopic eye BCVA from baseline to 12 weeks with refractive correction alone.

6.6.1.1 Primary Analysis

An analysis of variance will be performed to compare the change in VA from baseline to 12 weeks in the therapeutic and control groups. The primary objective will be assessed with the following hypothesis:

$$H_0: \beta_1 \geq 0$$

$$H_a: \beta_1 < 0$$

where β_1 is the coefficient from the following model:

$$Y = \beta_0 + \beta_1 * X_1,$$

where Y is the adjusted average change in BCVA in the amblyopic eye from baseline to 12 weeks, β_1 and X_1 are the coefficient and regression term for treatment arm (X_1 coded as therapy=1, control=0), respectively.

The hypothesis will be evaluated using a one-sided F-test for the coefficient associated with treatment group. A standard F-test will be used to determine if there is a significant difference in mean change from baseline between groups. The endpoint will be presented as average BCVA at baseline and 12 weeks, change in BCVA from baseline to 12 weeks in each treatment group, difference in BCVA change between treatment groups, two-sided 90% confidence interval of the difference, and p-value associated with the hypothesis test above. The endpoint will be considered met if the p-value for the coefficient is <0.05 .

The endpoint will be evaluated using the ITT population with no imputation for missing data.

Assessments from out of window visits will be considered missing in the primary analysis.

Supplementary analysis will be provided based on ITT with imputation, PP and AT cohorts.

The 24-week visit for participants in the control group who switch over to the therapeutic at the 12-week visit will not be a part of the primary analysis.

Statistical Analysis Plan		Page 17 of 23
Sponsor Luminopia	Study Luminopia One Amblyopia Vision Improvement Study	V

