4.1 Randomization

Participants will be randomized at the screening and enrollment visit. Randomization will be performed using a random permuted block design stratified by investigational site with a 1:1 allocation ratio (therapeutic group : control group). Randomized treatment will be assigned from the electronic database randomization assignment module.

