6.1.4 Statistical Significance

The primary efficacy and safety endpoints will be performed using one-sided tests and a 0.05 significance level. Any additional exploratory hypothesis testing will be performed at the two-sided 0.05 significance level. P-values will be rounded to three decimal places. If a p-value is less than 0.001 it will be reported as "<0.001". If a p-value is greater than 0.999, it will be reported as ">0.999".

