6.6.2 Primary Safety Endpoint

The co-primary analysis of safety will test if the mean change in fellow eye visual acuity of the therapeutic group from baseline to 12 weeks is non-inferior to the mean change in fellow eye visual acuity of control group within a margin of 0.10 logMAR. The formal hypothesis being tested are:

$$H_0: \mu_{\text{therapeutic}} - \mu_{\text{control}} \geq \delta$$

Statistical Analysis Plan		Page 18 of 23
Sponsor Luminopia	Study Luminopia One Amblyopia Vision Improvement Study	

$$H_a: \mu_{\text{therapeutic}} - \mu_{\text{control}} < \delta$$

where μ is the change from baseline (follow-up - baseline) for both the control and therapeutic participants and δ is the non-inferiority window of 0.10 logMAR. The statistical test is a two-sample one-sided T-test which will be done at the 0.05 level of significance. An upper 95% confidence limit for the difference will also be presented. The endpoint will be considered met if the p-value is < 0.05 .

The endpoint will be evaluated using the ITT population with no imputation for missing data. Assessments from out of window visits will be considered missing in the primary analysis. Supplementary analysis will be provided based on ITT with imputation, PP and AT cohorts, as described in the primary efficacy endpoint analysis.

In addition to the formal test on the mean change in fellow eye visual acuity, the primary safety endpoint will report the frequency and severity of all related Adverse Events (anticipated and unanticipated). Count of events, percent of participants who experienced an event, and an exact 95% confidence interval of the event rates will be presented for each treatment group by event type. No formal hypothesis testing will be performed. Event rates will be summarized for clinical interpretation. Safety analyses on Adverse Events will be based on the AT analysis cohort.

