6.8 Site Poolability Analyses

Data from this trial will be pooled across study site for the purposes of analysis. To demonstrate poolability of the primary endpoint data, the change in amblyopic eye BCVA between baseline and 12 weeks will be calculated for each participant. This value will be used as the dependent variable in a linear model. The independent predictors will be study site, treatment group, and a study site by treatment group interaction. If the interaction term is considered non-significant then the data will be pooled across site for the purposes of analysis. If the interaction term is considered significant then the analysis of the primary endpoint will have to be adjusted for study site. A significance level of 0.15 will be used for this analysis. Sites with fewer than 5 participants enrolled may be combined into one site for purposes of this analysis.

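### The primary efficacy analysis leaves out baseline BCVA and the stratification factor site, admits site only through an outcome-based test with no stated model, and describes its F-test in two incompatible ways

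*SAP*

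**What the plan says.** **Model.** Section 6.6.1.1 says "An analysis of variance will be performed to compare the change in VA from baseline to 12 weeks in the therapeutic and control groups". The equation has an intercept and a treatment term. The outcome is described as an adjusted average change, but the model has nothing to adjust for.

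**Site.** Section 4.1 randomises by a "random permuted block design stratified by investigational site with a 1:1 allocation ratio". Site is absent from the primary model. Section 6.8 fits site, treatment and their interaction to the primary outcome and tests the interaction at 0.15. It continues: "If the interaction term is considered significant then the analysis of the primary endpoint will have to be adjusted for study site". On small sites it says: "Sites with fewer than 5 participants enrolled may be combined into one site for purposes of this analysis".

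**Test.** Section 6.6.1.1 sets the alternative as a negative treatment coefficient and asks for a two-sided 90% confidence interval. It then says "The hypothesis will be evaluated using a one-sided F-test for the coefficient associated with treatment group", and next "A standard F-test will be used to determine if there is a significant difference in mean change from baseline between groups". The endpoint is met if p<0.05. Section 6.1.4 says "The primary efficacy and safety endpoints will be performed using one-sided tests and a 0.05 significance level". For the fellow-eye endpoint, section 6.6.2 says "The statistical test is a two-sample one-sided T-test which will be done at the 0.05 level of significance".

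**The concern.** There are three weaknesses in one specification.

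1. **Baseline BCVA.** It is known for every analysed child, because section 6.6.1.2 excludes those without it. Section 6.6.1.3 provides for a search for baseline covariates associated with change, and section 6.7 lists baseline VA as a factor of interest. Leaving it out of the primary model gives up precision for no saving.

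2. **Site.** The randomisation is stratified by site, so the analysis should reflect site from the start. Here a test on the primary outcome decides whether it does. Once that test is triggered, the SAP does not say whether adjustment means a site main effect or a model that keeps the interaction, nor how sites would be weighted. A main effect alone would not address the interaction that triggered it. Pooling of small sites is optional, and section 6.8 does not say whether the check applies at the interim, so the two looks could use different models.

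3. **Test.** An F-test on one degree of freedom has no direction. Its p-value is twice the one-sided p-value when the effect is favourable, and it can fall below 0.05 when the effect is in the wrong direction. The two F-test sentences therefore give different p-values for one decision rule.

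**Working it through.** **Inputs from the SAP (section 5).** Difference 0.075 logMAR; SD of change 0.140; one-sided alpha 0.05; beta 0.10; looks at t = 0.75 and 1; alpha spending 0.05·t²; beta spending 0.10·t; 132 evaluable children.

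**Assumptions, because the SAP gives no figure.** Correlation of baseline with change, number of sites, and share of variance between sites.

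**Step 1: reproduce the design (binding futility).**
- Interim alpha = 0.05 × 0.75² = 0.0281, so interim Z = 1.909.
- Interim futility Z = 1.216; final Z = 1.639; required drift 3.066.
- N = 4 × 0.140² × 3.066² / 0.075² = 131.0 (stated 132).
- Power at 132 is 90.2%. Futility stop under no effect is 88.8% (stated about 89%).

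The stated sample size thus rests on an unadjusted one-sided 0.05 test.

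**Step 2: add baseline BCVA.** Residual variance is multiplied by 1 − r².

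| Assumed r | Variance factor | Power at 132 |
|---|---|---|
| 0 | 1.00 | 90.2% |
| 0.30 | 0.91 | 92.4% |
| 0.45 | 0.80 | 94.9% |

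**Step 3: ignore or include site.** Power is before any loss of degrees of freedom.

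| Assumed between-site share | One-sided level, site ignored | Power, site ignored | Power, site included |
|---|---|---|---|
| 0 | 5.0% | 90.2% | 90.2% |
| 0.05 | 4.6% | 90.8% | 91.4% |
| 0.10 | 4.1% | 91.4% | 92.6% |

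Ignoring the stratum makes the test conservative. Including it gains 0 to 1.2 points.

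**Step 4: simulate the 0.15 check.** Single-look trials of about 132 children, 10 or 20 unequal sites, blocks of 4, sites under 5 pooled, between-site share 0 to 0.10, no true interaction, 12,000 trials per setting.
- The check fires in 14–15% of trials.
- If adjustment then means a site main effect, the verdict changes in 1–2% of the triggered trials.
- If it means an equal-site-weighted effect from the interaction model, the verdict changes in 5–14% of them. In those trials the one-sided level is 6.3–7.7% and power 82–90%, against 91–94% unadjusted.
- Over all trials the level stays at 4.0–5.4%.

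These power figures are for a single look and are not comparable with the sequential 90.2%.

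A second simulation used 11 or 20 equal sites, between-site share 0 to 0.20 and r = 0.3. The check fired in 15–16% of trials and the overall level was 3.4–5.5%. With no site differences, a model with baseline and site raised single-look power from 91.3% to 93.5% (11 sites) and from 92.2% to 93.8% (20 sites), after the loss of degrees of freedom.

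**Step 5: take the F-test literally.** The two-sided p-value is compared with 0.0281 at the interim and 0.05 at the end, with success only in the favourable direction. The one-sided level is 2.8%, power at 132 is 86.2%, and 90% power needs 149.6, about 150 children. If all boundaries are instead re-solved at one-sided 0.025, power is 83.7% and about 161 children are needed. The loss is 4.0 to 6.5 points, depending on the reading.

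**The case against.** The unadjusted comparison is valid, and its sample size was built on the unadjusted SD, so analysis and design agree. The gain from baseline rests on correlations that the SAP does not give, and the range includes zero. Section 6.6.1.3 allows for finding no predictive covariate, and section 6.7 treats baseline VA only as an exploratory subgroup factor. All of this stands, and the omission is therefore forgone precision rather than an error.

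On site, the natural reading of adjustment is a site main effect. On that reading the verdict changes in 1–2% of the 14–15% of trials triggered, roughly 0.1–0.3% of all trials. The larger figures need an estimator that the SAP never names, and they are conditional on the check firing. The check's own model and level are stated. This also stands. It limits the demonstrated harm but does not supply the missing adjusted model.

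On the test, the directional hypothesis, the 90% interval, section 6.1.4 and the one-sided setting in section 5 all show that one-sided 0.05 is meant. A one-degree-of-freedom F statistic is the square of t, so the difference from section 6.6.2 is largely one of label. The intent is indeed clear, and the power loss arises only if the printed p-value is used without halving and a check of direction. A confirmatory decision rule should not depend on that inference.

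**Conclusion.** The concern holds, as something that should be corrected rather than a flaw that invalidates the trial. There is no power shortfall in the planned unadjusted test and no material inflation of type I error on average. What is firmly established from the text is that the two F-test sentences conflict, that the site-adjusted primary model is undefined, and that its use depends on outcome data. The size is conditional: 0 to about 5 points of power forgone on baseline for correlations of 0 to 0.45; 0 to 1.2 points on site for between-site shares of 0 to 0.10; and 4.0 points lost if the F p-value is applied as printed at the design's boundary levels.

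**What to change.** - **Section 6.6.1.1:** prespecify change in BCVA = treatment + baseline amblyopic-eye BCVA + site, all as fixed effects. State that sites with fewer than 5 participants will be combined into one, so that pooling is no longer optional.
- **Test:** delete both F-test sentences. Test the treatment coefficient with a lower-tail one-sided t-test against the group sequential boundary (interim one-sided p about 0.028; final value from the SEQDESIGN output).
- **Section 6.8:** delete the sentence that makes site adjustment depend on the 0.15 test, and report the interaction descriptively.
- **Sensitivity:** keep the unadjusted comparison as a sensitivity analysis. The same adjustment for the fellow-eye test in section 6.6.2 is optional.

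The cost is SAP wording and two model terms, with no new data. The drawback is the degrees of freedom used by site: with 10 to 20 sites assumed and no site differences, the simulated loss is 0.3 to 0.5 points of power.

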6.6.4.3 VA at 4 and 8 Weeks

The primary endpoint analysis will be repeated for mean change in amblyopic eye BCVA from baseline to 4 and 8 weeks of treatment with Luminopia One will be compared to continued refractive correction. Mean change and 95% confidence intervals will be presented. Sensitivity and supplementary analyses may be performed as needed. Subjects with available data at baseline and an in-window follow-up visit will be included in the analysis.

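### SAP 6.6.1.1 describes the primary efficacy test both as one-sided and as a standard (two-sided) F-test; the test wording is wrong, the sample size is not.

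*SAP*

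**What the plan says.** SAP 6.6.1.1 states H_0: beta_1 ≥ 0 against H_a: beta_1 < 0, with therapy coded 1 and control 0, so a negative coefficient favours the device. It then gives two sentences on the test. One carries the direction: "The hypothesis will be evaluated using a one-sided F-test for the coefficient associated with treatment group".

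The other, which comes straight after it, names no direction: "A standard F-test will be used to determine if there is a significant difference in mean change from baseline between groups".

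The outputs include a "two-sided 90% confidence interval of the difference" and, as the reported test result, the "p-value associated with the hypothesis test above". The decision rule is: "The endpoint will be considered met if the p-value for the coefficient is <0.05".

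Elsewhere the plan is consistent. SAP 6.1.4 says: "The primary efficacy and safety endpoints will be performed using one-sided tests and a 0.05 significance level". Section 5 justifies a one-sided superiority test and sizes the trial with a one-sided alpha of 0.05 and 90% power. Sections 5 and 6.9.2 specify two looks, the first at 75% of participants, with alpha and beta spent by power functions (rho 2.0 and 1.0).

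**The concern.** A standard F-test with one numerator degree of freedom rejects for large t² whatever the sign of t. At p < 0.05 it puts 0.025 in each direction, whereas the stated hypothesis puts the full 0.05 in the direction of benefit. A programmer who takes the default F p-value from an ANOVA table would be following one sentence of the plan and breaking the one before it. The phrase one-sided F-test does not settle the matter, because it does not say how the sign enters.

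The wording matters because it belongs to the decision rule for the primary efficacy endpoint, one of the two conditions for study success in SAP 6.6.3. The same paragraph also tests against a flat 0.05 and does not mention the group sequential boundary, although the design has two looks.

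**Working it through.** **Inputs (SAP sections 4.1 and 5).** Difference 0.075 logMAR, SD 0.140, 1:1 allocation, one-sided alpha 0.05, beta 0.10, looks at information 0.75 and 1.0, alpha spending 0.05·t², beta spending 0.10·t. Whether futility is binding is not stated, so both cases are computed.

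**1. Reproduce the plan's figures.**
- Alpha spent at the interim: 0.05 × 0.75² = 0.0281, so the interim efficacy bound is z = 1.909.
- Beta spent at the interim: 0.10 × 0.75 = 0.075.
- With binding futility, the interim futility bound is z = 1.216 and the final bound is z = 1.639 (nominal one-sided p 0.0506). The required drift is 3.066.
- N = 4 × (0.14 × 3.066 / 0.075)² = 131.0, which is 132 with equal arms. The probability of stopping for futility under no effect is 88.8%. The SAP states 132 and approximately 89%.
- Alternatives do not reproduce 132. One-sided with non-binding futility needs 138.6. A two-sided 0.05 design needs 160.7 (binding) or 168.6 (non-binding).

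**2. Range of results on which the two sentences disagree (single final look, 132 participants, 130 df).**
- SE = 0.14 × √(4/132) = 0.02437.
- One-sided 0.05: t < -1.657, a difference beyond -1.657 × 0.02437 = -0.040 logMAR.
- Standard F at 0.05: F > 3.91, so |t| > 1.978, a difference beyond -1.978 × 0.02437 = -0.048 logMAR.
- The final group sequential level (0.0506) gives the same range to three decimals.
- Example: t = -1.8, difference -0.044. The one-sided p is 0.037 and the 90% CI is -0.084 to -0.003 (met). The standard F p is 0.074 (not met).

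**3. Operating characteristics at N = 132.** Drift = 0.075 / 0.02437 = 3.077, binding futility. The probability of claiming benefit is:

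| Rule | Power at 0.075 | Early success at 0.075 | No true effect |
|---|---|---|---|
| One-sided p at group sequential levels | 90.2% | 77.5% | 5.0% |
| Standard F p at the same levels (z = 2.196, 1.954) | 86.2% | 68.1% | 2.8% |
| Standard F p at flat 0.05, both looks | 87.1% | 76.0% | 3.5% |

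At group sequential levels, the loss from using the standard F p depends on the true difference: 54.9% to 45.6% at 0.045 logMAR, and none to speak of at 0.119 logMAR (99.8% either way). Over the SDs in SAP Table 1, at a true difference of 0.075, power is 94.1% versus 91.5% (SD 0.128) and 79.9% versus 73.3% (SD 0.166).

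**4. The flat 0.05 threshold.** With a correct one-sided p-value, testing at z = 1.645 at both looks gives a one-sided type I error of 6.3% if futility is binding and 7.1% if it is not, against the overall 5% set in section 4. The nominal levels that hold 5% are 0.028 at the interim, and at the final look 0.051 (binding) or 0.040 (non-binding).

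**The case against.** The strongest reply is that the plan already resolves the ambiguity. The directional hypotheses, the preceding sentence, the 90% interval, the reference back to the stated hypothesis test, SAP 6.1.4 and the section 5 design all point to one-sided 0.05, against one loose sentence. That is right as to intent, and it makes every power figure above for the standard F-test conditional. It does not make the sentence correct: it names a different test inside the primary decision rule.

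Three stronger readings are tempting and are not supported:

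- **The trial is undersized.** A reader might infer that about 162 participants are needed (160.7, rounded to equal arms). That would follow only if a two-sided 0.05 test were intended, and nothing else in the plan says so.
- **Success could be declared when control does better.** At t = +2.0 (control better by 0.049 logMAR) the standard F p is 0.048, while the one-sided p is 0.976. Calling this met would require ignoring the alternative hypothesis in the same section.
- **The 4- and 8-week comparisons are affected.** SAP 6.6.4.3 says: "The primary endpoint analysis will be repeated for mean change in amblyopic eye BCVA from baseline to 4 and 8 weeks". But SAP 6.6.4 makes any secondary comparison exploratory, and SAP 6.1.4 says: "Any additional exploratory hypothesis testing will be performed at the two-sided 0.05 significance level". The 95% intervals in 6.6.4.3 agree. A two-sided p-value is the right one there, and no edit is needed.

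It is also fair to say that the flat 0.05 is a separate matter from sidedness. It is raised here because rewriting the test sentence alone would leave a correct p-value compared with the wrong threshold.

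**Conclusion.** The point holds as an error in the wording of the test. SAP 6.6.1.1 gives two incompatible descriptions of the primary efficacy test, and the standard F-test sentence is the one that conflicts with the rest of the plan. The sample size of 132 is correct for the one-sided test.

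If the one-sided p-value is used, as the plan otherwise indicates, the planned 90% power holds. If the standard F p-value were used, results between about -0.040 and -0.048 logMAR at the final look would change from met to not met. Power at 0.075 logMAR would be about 86% at the group sequential levels, or about 87% at a flat 0.05. The error would be conservative for claims of benefit. These figures assume SD 0.14 and binding futility; the SAP does not state the latter, but its figure of 132 implies it.

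The linked error goes the other way. The flat 0.05 in 6.6.1.1, and the 0.05 level in 6.1.4 as it applies to the primary efficacy test, do not refer to the spending boundary. Applied at both looks they give a type I error of about 6.3% to 7.1%. Both should be corrected before any interim data are examined.

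**What to change.** 1. In SAP 6.6.1.1, delete the standard F-test sentence.
2. Replace the one-sided F-test sentence with: *beta_1 will be tested with a one-sided t-test from the model (H_a: beta_1 < 0), with p-value P(T < t_observed).*
3. In SAP 6.6.1.1, and in 6.1.4 for the primary efficacy test, replace the flat 0.05 criterion with: *The efficacy endpoint is met if the one-sided p-value is below the nominal level of the group sequential efficacy boundary at that analysis (overall one-sided alpha 0.05).* With the stated settings the interim level is about 0.028. The final level is about 0.051 if futility is binding, as N = 132 implies, or about 0.040 if it is non-binding.
4. State in SAP 6.9.2 whether the futility boundary is binding.

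The cost is a few sentences. If futility is declared binding, N, alpha and the design do not change. If it is declared non-binding, the same calculation gives 138.6 rather than 131.0 for 90% power, so the stated power at 132 would have to be revisited.

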3.4 Safety Reporting

3.4.1 Adverse Events

The participant and parent(s) will be asked about anticipated and unanticipated adverse events at each visit and phone call. The frequency of known and unknown adverse events will be summarized for all participants.

4 Study Design

The proposed study is a multi-center randomized, controlled, masked, clinical trial which compares mean change in amblyopic eye BCVA from baseline with Luminopia One (“therapeutic”), to refractive correction (“control”). One-hundred and forty participants ($n = 140$) aged 4-7 years (inclusive) will be enrolled. Participants will be randomized 1:1 to the “therapeutic group”, to use Luminopia One, or the “control group”, to undergo continued refractive correction, for 12 weeks of treatment.

A group sequential design with a single interim analysis will be used to allow stopping for either early success or futility in both primary safety and efficacy endpoints. The interim analysis will be conducted after 75% of participants have completed their 12-week follow-up visit. The overall Type I error rate was set at 0.05.

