6.6.3 Study Success

The study will be considered a success if both the primary efficacy and primary safety endpoints are passed. The 12-week visit measurements in the therapeutic and control groups will determine success and failure of the trial for both primary safety and efficacy endpoints. Measurements from the 24-week visit, for participants in the control group who switch over to the therapeutic after the 12-week visit will not be part of the primary analysis and will not define study success.

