6.9.2 Group Sequential Design

A group sequential design will be employed to allow for early stopping due to either success (rejecting the null hypothesis) or futility. The goal of the group sequential design is to conserve precious time and resources and prevent unnecessary enrollment of participants if there is no observed difference in effect between groups or if there is a significant effect in favor of Luminopia One. It is important to allow for early stopping for success since there is a real possibility the therapeutic could perform significantly better than expected.

Boundaries for both alpha and beta will be calculated using a power cumulative error spending function. The mathematical form of this spending function is:

$$E(t, \rho) = \begin{cases} 1 & \text{if } t \geq 1 \\ t^\rho & \text{if } 0 < t < 1 \\ 0 & \text{otherwise} \end{cases}$$

where ρ is the power parameter and t is the information fraction.

For beta spending, rho was set to 1.0 which results in a spending function much like the Pocock method (i.e. equal spending between the interim and final analyses). For alpha spending, rho was set to 2.0 resulting a spending function somewhere between that found for the O'Brien-Fleming method and the Pocock method.

The planned interim analysis will be conducted after 75% of participants, of the re-estimate sample size, reach their 12-week visit and will also involve an analysis of the primary safety and efficacy endpoint, and a report of the frequency and severity of all related Adverse Events (anticipated and unanticipated). All endpoint analyses will be conducted simultaneously on the same data snapshot.

Minimizing Bias

The interim analysis will be designed to optimize usage of time and resources while controlling the Type I and II error rates and minimizing operational bias, in accordance with FDA's guidance on Adaptive Designs for Medical Devices.

Type I and II Error Rates

Statistical Analysis Plan		Page 22 of 23
Sponsor Luminopia	Study Luminopia One Amblyopia Vision Improvement Study	

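### The primary success rules use a flat one-sided p<0.05 with no look named, which conflicts with the alpha-spending design (p≤0.0281 at the 75% interim)

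*SAP*

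**What the plan says.** Three sections give the decision rule for the two endpoints that define success.

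- Section 6.1.4: "The primary efficacy and safety endpoints will be performed using one-sided tests and a 0.05 significance level".
- Section 6.6.1.1, efficacy: "The endpoint will be considered met if the p-value for the coefficient is <0.05".
- Section 6.6.2, fellow-eye non-inferiority: "The endpoint will be considered met if the p-value is < 0.05".

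Section 6.6.3 builds on these: "The study will be considered a success if both the primary efficacy and primary safety endpoints are passed".

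The design sections describe a two-look trial. Section 4 sets a single interim at 75% "to allow stopping for either early success or futility in both primary safety and efficacy endpoints" and adds: "The overall Type I error rate was set at 0.05". Section 5 gives the spending parameters (rho=2 for alpha, rho=1 for beta). Section 6.9.2 repeats them, says "Boundaries for both alpha and beta will be calculated using a power cumulative error spending function", and confirms that efficacy and safety are both tested at the interim: "All endpoint analyses will be conducted simultaneously on the same data snapshot". It then relies on alpha spending as the means of controlling the overall Type I error.

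No section at hand prints a nominal boundary for either look, limits the p<0.05 rule to the final analysis, or says whether the futility stop is binding. Section 6.9.1 is not in the available text.

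**The concern.** The rules in 6.1.4 and 6.6 do not carry out the design in 6.9.2. For an interim p between 0.0281 and 0.05 they give opposite answers, and the SAP does not say which governs. The interim is run by the CRO and the sponsor, so the choice could be made with the data in view. At stake is the 5% overall error that Section 4 states and 6.9.2 claims to protect, for both tests on which study success depends.

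**Working it through.** **Inputs (all from the SAP).** One-sided alpha 0.05; beta 0.10; interim at t = 0.75; alpha spending 0.05·t²; beta spending 0.10·t; efficacy difference 0.075 logMAR; SD 0.14; 1:1 allocation; 132 evaluable participants (Section 5). Fellow eye: SD 0.10, margin +0.10, expected difference −0.05 − (−0.02) = −0.03. The two test statistics are treated as bivariate normal with correlation √0.75.

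**1. Reproducing the plan's own figures.** Solving the two-look design gives:

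| Futility boundary | Total N for 90% power | P(futility stop, no effect) |
|---|---|---|
| Binding | 131.0, i.e. 66 per arm = 132 | 88.8% (89.0% at N=132) |
| Non-binding | 138.6 | 90.2% |
| SAP states | 132 | about 89% |

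The plan's figures are those of a binding futility boundary.

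**2. Interim success boundary.** 0.05 × 0.75² = 0.028125, so one-sided p≤0.0281 (z≥1.909). The flat rule needs only z>1.645.

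**3. Where the sections disagree.** At 75% of 132 there are 99 participants. The standard error is 0.14 × √(4/99) = 0.0281 logMAR.

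- The disputed zone runs from 1.645 × 0.0281 = 0.046 to 1.909 × 0.0281 = 0.054 logMAR of observed advantage.
- Under no effect its probability is 0.05 − 0.0281 = 2.2%.
- Under the design effect the interim z has mean 0.075/0.0281 = 2.665, and the probability is Φ(1.909 − 2.665) − Φ(1.645 − 2.665) = 7.1%.

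**4. Final boundary.** At N=132 the interim futility boundary is z = −1.440 + 2.665 = 1.226 (p = 0.110, or 0.034 logMAR at n=99). The final level that spends exactly the remaining alpha is p = 0.0511 if futility is binding and p = 0.0402 if it is not.

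**5. Type I error by rule.** Without futility, the error is 1 − P(Z₁ < u₁, Z₂ < u₂). With futility obeyed, it is P(Z₁ ≥ u₁) + P(l₁ ≤ Z₁ < u₁, Z₂ ≥ u₂), where l₁ = 1.226.

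| Rule (interim / final) | Futility obeyed | Futility not enforced |
|---|---|---|
| 0.05 / 0.05 | 6.24% | 7.09% |
| 0.0281 / 0.05 | 4.95% | 5.80% |

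A simulation with actual t-tests (50 then 66 per arm, no futility) gives 7.1% and 5.8%.

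**6. Fellow eye.** Section 5 derives a boundary from the efficacy inputs only. The same beta spending applied to the fellow-eye test (n=132, SD 0.10, margin 0.10) would put the interim futility boundary at z = 5.03 for a true difference of −0.03, and at z = 3.54 for zero difference. Both lie above the success boundary of 1.91, so the efficacy futility rule cannot be carried over. With no futility boundary of its own, this test falls in the right-hand column: up to 7.1% under the flat rule, or 5.8% with 0.0281 then 0.05. Those ceilings apply at a true difference of +0.10.

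**The case against.** The best reply is that 6.6 never mentions the interim. The spending function, rho, look time and total alpha are all written down, so the specific interim rule should be read over the general one: spending boundary at the interim, p<0.05 at the final. On that reading efficacy error is 4.95%, and p<0.05 is slightly stricter than the exact final level of 0.0511. The figures in Section 5 also imply binding futility, which leaves only a missing cross-reference. Two further points: study-level error requires both endpoints to pass, and Section 6.9.1 may print the boundaries.

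Much of this stands. The consistent reading is available, and the 6.2% to 7.1% arises only if the spending boundary is not used at the interim. Three things remain.

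- Nothing in the text limits p<0.05 to the final look. Boundaries printed in 6.9.1 would not change 6.1.4 and 6.6, which do not refer to them.
- The text only permits a futility stop. If the sponsor continues past the boundary and then uses p<0.05, error is 5.8%.
- The fellow-eye gap survives even the favourable reading. Requiring both endpoints softens it: with the endpoints taken as independent and efficacy futility obeyed, false study success at +0.10 is just above 5% at an efficacy effect of 0.075. It reaches 5.8% at 0.119, the difference that Section 5 calls possible.

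**Conclusion.** The concern holds. The success rules as written do not implement the sequential design and conflict with it for any interim p between 0.0281 and 0.05. Applied at both looks, they give 6.2% (futility obeyed) to 7.1% (not enforced) per endpoint instead of 5%. On the most favourable reading, efficacy is held at 4.95% only if futility is binding, and the fellow-eye test can reach 5.8%.

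The interim 0.0281, the non-binding 0.0402, and the 7.1% and 5.8% depend only on t = 0.75 and the spending function. The 6.2%, the 4.95%, the 0.0511 and the logMAR zone also assume 132 evaluable participants and, where it enters, SD 0.14. Section 6.9.2 refers to a re-estimated sample size that the available text does not explain; if N changes, those figures must be recomputed. This should be corrected before the interim, because it is the decision rule for both primary endpoints.

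**What to change.** In 6.1.4, 6.6.1.1 and 6.6.2, replace the flat rule with boundaries for each look, recomputed at the actual information fraction, and refer to 6.9.2.

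- **Efficacy:** met at the interim if one-sided p≤0.0281 (t = 0.75); met at the final if p<0.05. Add a sentence that the efficacy futility stop is binding. If the sponsor prefers it non-binding, use p≤0.0402 at the final and restate the power at 132.
- **Fellow eye:** met at the interim if p≤0.0281, at the final if p≤0.0402. If a futility stop is wanted for this test, derive its boundary separately and state that it is binding.

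The interim level moves with timing: 0.05 × 0.70² = 0.0245 and 0.05 × 0.80² = 0.0320. With binding futility and a final p<0.05, efficacy error stays at 4.97% and 4.91% in those two cases.

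The cost is SAP wording only. Efficacy power at 132 is 90.1% with binding futility and final p<0.05, or about 89% with 0.0402. The fellow-eye test at 0.0281/0.0402 keeps more than 99.9% power at a difference of −0.03 and also at zero. No extra participants or visits are needed.
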